instructed to complete the voice recording in a private location and to ensure no other individuals are present or speaking during the recording. Participants will be reminded to pause, stop, or restart the recording if another person enters the space. Participants will also be reminded that the voice recording is optional--they may skip voice recording submission without penalty and still receive compensation. Audio will be downloaded from Expiwell, uploaded to Stronghold, then deleted from Expiwell's storage. The audio housed in Stronghold will be deleted after they are transcribed and vetted for accuracy by study staff. A research assistant will monitor responses to the EMA on a daily basis (including the voice recording, where a transcript will automatically become available through Expiwell's AWS service). Any reportable events that are observed will be reported to the PI, and the PI will be available to meet, if necessary, to review concerns regarding a particular participant or any problems that may arise for participants.

Weekly assessments: During first 4 weeks of intervention period (i.e., Recommended Modules), participants will be asked to complete a survey every week. The survey consists of 2 scales (PHQ-9 and GAD-7) as well as 3 items from interoceptive awareness scale, 3 items from de-centering scale, 3 items from perseverative thinking scale, and 1 item from theory of distress scale. Each survey will take 4-5 minutes, with a total of 16-20 minutes over the 4 week period.

Wearable device: Also during the first 4 weeks of intervention period (i.e., Recommended Modules), data will be collected from a Fitbit from each participant. Data collected include total sleep time, sleep onset latency, REM and non-REM sleep duration, sleep/wake variability, and resting heart rate. Each participant will be mailed a Fitbit from the study team along with a pre-paid return envelope at the enrollment in the study. These devices will be assigned to participants and linked to de-identified study accounts only. Participants will be instructed to wear the Fitbit device daily, before going to bed, for the entire 4-week period. At the end of the intervention, participants will be asked to return the Fitbit using the pre-paid return envelope.

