Data analysis: Feasibility, acceptability, and preliminary effects will be assessed using data from the T1, T2, and T3 surveys as well as EMA responses. Qualitative data analysis will also be performed for the exit-interviews and voice recordings to further qualify our findings after transcription and deidentification. Exit interviews will be transcribed using Dedoose (already vetted through OIT), while EMA voice recordings will be transcribed automatically through Expiwell's AWS service. Additionally, recruitment and retention rates, completion of weekly modules, adherence to daily EMA and EMI prompts, weekly session attendance, and other engagement metrics from the application (e.g., frequency of EMI-triggered vs. self-initiated practice use, time spent in modules) will be used to inform study and intervention feasibility.

- 6.3 We will take all reasonable precautions to prevent adverse events to participants. As a meditation-based intervention, a number of actions have been taken to minimize meditation-related risks at different stages of the study. During the pre-enrollment stage, individuals with severe mental

illness that could preclude regular class attendance or impact group participation (i.e., symptomatic, untreated bipolar disorder or a history of psychosis and/or schizophrenia) are excluded from the study. During treatment, meditations are created to be relatively short and interspersed with dyads and reflections to minimize probability of risk. Developing strategies for working with physical and emotional discomfort is also an explicit goal of the program.

No drugs will be administered as part of this study. The only devices used are a) the participant's personal cell phone with the intervention content loaded through the Expiwell app and b) a wearable device Fitbit, which is commercially available and FDA-cleared for general wellness monitoring; it will be used solely to collect sleep and physiological data.

For all assessments and guides used for data collection, please refer to the document named "Compiled measures_GEM.docx".

6.4 A list of all data that and how they will be collected during the study is listed below:

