Self-report data on feasibility, acceptability, and preliminary efficacy: Data on feasibility and acceptability as well as preliminary efficacy of the intervention on study outcomes (including mental health, functional impairment, emotion regulation, loneliness, mindfulness, self-compassion, stress, sleep, phone use, overall well-being, etc. – refer to Section 6.2 for full list of scales measured at each time point) will be collected via Qualtrics at baseline, post-intervention, 3-month follow-up, and weekly assessments during the first 4 weeks of intervention period (i.e., Recommended Modules).

EMAs: Daily self-reports on stress, mood, and emotional states will be collected on the Expiwell application. Furthermore, voice recordings for a "daily journal" will be collected during the last EMA of the day. Participants will be reminded that the voice recording is optional--they may skip voice recording submission without penalty and still receive compensation.

App engagement metrics: Frequency and duration of EMI-triggered and self-initiated mindfulness practice sessions will be collected on Expiwell.

Sleep metrics: Continuous objective data on sleep metrics (e.g., sleep latency, REM/non-REM sleep, sleep fragmentation, total sleep time, sleep efficiency) will be collected using wearable devices (i.e., Fitbits).

Semi-structured interviews: Qualitative feedback on intervention experience, feasibility, acceptability, and suggestions for improvement will be collected through a semi-structured Zoom interview with an RA.

6.5 Participants will complete a 3-month post-baseline follow-up survey after the 4-6-week intervention (4 weeks recommended, 2 weeks optional/bonus). Similarly to post-intervention survey, this assessment will collect self-report data on mental health, functional impairment, emotion regulation, loneliness, mindfulness, self-compassion, stress, sleep, phone use, overall well-being, etc. (refer to Section 6.2 for full list of scales measured 3-month follow-up).

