11.0 Vulnerable Populations

11.1 N/A

12.0 Local Number of Subjects

12.1 We anticipate enrolling 44 *participants in the single-arm trial*.

12.2 A larger number of young adults will be screened for eligibility, and 44 participants will be recruited to enroll in the single-arm trial. From these 44 participants, we aim to have at least 35 participants (i.e., approximately 80%) who complete all intervention procedures and follow-up assessments. Screening more participants ensures that we can meet the target enrollment despite ineligible candidates, and enrolling more ensures that we collect enough data points even with potential withdrawals.

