- 13.2 The source of participants will be local and online communities where individuals with lived experiences of early life adversities and mental health challenges may be present. These communities include, but are not limited to social networks, LGBTQ+ groups, foster care and youth residential programs, and networks that provide support for survivors of abuse and violence.
- 13.3 Potential participants will be identified by having them self-report their age, experiences of early life adversities, and depression or anxiety symptoms through the screening Qualtrics survey. The research team will contact individuals for further screening (i.e., schedule Zoom screening interview) if they are deemed potentially eligible from the screening survey (see Sections 10.1 and 10.2).
- 13.4 Other than the email draft and written script described in Section 13.1, recruitment materials will include flyers and graphics for social media posts. Each material will provide a brief study description, eligibility criteria, and contact information. Please refer to the files titled "Recruitment_GEM.docx" for flyers and social media graphics. Furthermore, recruitment materials created by OpenClinica will be submitted to the IRB for review when they are created, after a contract is finalized.
- 13.5 Participants will only be compensated for the study components that they choose to complete. If a participant withdraws from the study early, they will not be compensated for the study components that are incomplete. Compensation will be provided through Amazon gift cards. Total possible compensation for participants is \$168:

Study Procedure	Compensation	Compensation period
-----------------	--------------	---------------------

Baseline assessment (T1)	\$25	Paid after survey completion
Ecological momentary assessment (during the first 4 weeks of intervention period; i.e., recommended modules)	Maximum of \$56: \$2/day for completing at least 2 of 3 daily EMA prompts over a maximum of 28 days (i.e., 4-weeks)	Paid in a single installment at the end of Week 4
Weekly assessments (during the first 4 weeks of intervention period; i.e., recommended modules)	Maximum of \$12: \$3 for completing each assessment, once a week over 4 weeks	
Post-intervention assessment (T2)	\$25	Paid after (1) survey/interview completion AND (2) Fitbit device is returned to the study team
Exit interview (T2)	\$25	
Follow-up assessment (T3)	\$25	Paid after survey completion

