Pre-Post Changes (Clinical Outcomes) As a single-arm trial, we will use repeated measures ANOVA to assess preliminary changes in the primary clinical targets of depression (e.g., measured via PHQ-9) and anxiety (e.g., measured via GAD-7) from T1 to T2 (and T3 follow-up), characterizing within-group effect sizes using Cohen's *d*. To model individual clinical trajectories, we will use mixed-effects modeling with time entered as a fixed effect and participant as a random effect, incorporating relevant baseline covariates (e.g., age, gender, ELA severity).

EMA/Longitudinal Data Analysis

We will leverage the high-density EMA data using linear mixed-effects models to assess within-person, day-to-day, and moment-to-moment associations. Specifically, we will use time-lagged

analyses to evaluate the immediate, temporal impact of intervention engagement. For example, we will model whether the completion of an audio module at time t predicts significant reductions in momentary negative affect, anxiety, or perceived stress at the subsequent EMA prompt (time $t+1$). Additionally, we will visualize the interrelations between momentary stress, engagement with audio modules, and subsequent mood fluctuations via temporal network models.

To assess **momentary mechanisms**, we will utilize 1-1-1 Multilevel Structural Equation Modeling (MSEM). We will test whether momentary activation of specific psychological states (e.g., interoception, cognitive defusion, or acceptance/willingness) measured immediately post-EMI significantly mediates the relationship between EMI engagement at time t and reductions in negative affect at the subsequent EMA prompt (time $t+1$). We will conduct mediation analysis to understand which mechanism carries the largest indirect effect on symptom reduction. Additionally, we will visualize the interrelations between daily stressors, momentary mechanism activation, and subsequent mood fluctuations via temporal network models.

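### The weekly PHQ-9 and GAD-7 are collected as efficacy data, but no analysis names them and the symptom mixed model does not say which visits enter

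*Protocol*

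**What the plan says.** **Collection.** Under Weekly assessments, Protocol 6.2 states that during the four recommended weeks "participants will be asked to complete a survey every week". The survey carries both symptom scales whole ("The survey consists of 2 scales (PHQ-9 and GAD-7", followed by selected mechanism items). Section 13.5 confirms the count by paying, in dollars, "3 for completing each assessment, once a week over 4 weeks".

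**Purpose.** Protocol 6.4 says that self-report data on feasibility, acceptability and preliminary efficacy come from surveys "at baseline, post-intervention, 3-month follow-up, and weekly assessments during the first 4 weeks of intervention period". The weekly surveys are therefore listed as an efficacy source.

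**Analysis.**
- Protocol 6.2, Data analysis: "Feasibility, acceptability, and preliminary effects will be assessed using data from the T1, T2, and T3 surveys as well as EMA responses". The weekly surveys are not in this list.
- SAP, Pre-Post Changes (Clinical Outcomes): repeated measures ANOVA of PHQ-9 and GAD-7 "from T1 to T2 (and T3 follow-up", with Cohen's d. The next sentence adds a mixed model for individual trajectories, with time fixed and participant random, and does not list its visits.
- Protocol 17.1 describes the same mixed model, also without listing visits.
- The SAP's EMA and mediation models use momentary measures and do not mention the weekly scales.

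Neither document gives a missing-data method for T2 or T3.

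**The concern.** The two scales that the SAP treats as its primary clinical targets can be observed on up to seven occasions (T1, four weekly forms, T2, T3), but the stated analyses name only three.

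This matters mainly for people who leave early. Someone who stops after Week 2 and returns for neither T2 nor T3 contributes only a baseline score to a likelihood model on T1-T3, and nothing to a standard repeated measures ANOVA. The weekly forms are the only repeated PHQ-9 and GAD-7 evidence on how that person was doing. Loss linked to worsening is plausible here, because Protocol 15.1 lists increased depression and anxiety among the reported effects of meditation. Section 6.1 says the preliminary outcomes may inform future studies, so the estimate at stake is the one that would be carried forward.

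**Working it through.** **1. Planned completers.** Protocol 12.2 states "44 participants will be recruited to enroll in the single-arm trial" and aims for "at least 35 participants (i.e., approximately 80%) who complete all intervention procedures and follow-up assessments". Check: 0.80 × 44 = 35.2, and 35/44 = 79.5%. The plan's figure reproduces.

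**2. Forms available.**
- All participants: 44 × 4 = 176 per scale at most.
- Lost at the planned completion: 44 − 35 = 9, so at most 9 × 4 = 36 forms (36/176 = 20%).
- Lost if the SAP's retention benchmark (above 70% at T2) is just met: 0.70 × 44 = 30.8, so at least 31 stay and at most 13 leave. That gives at most 13 × 4 = 52 forms (52/176 = 30%).
- These are upper limits. If those who leave do so during Weeks 1-4 with 0 to 3 forms each (assumed mean 1.5), the counts are 9 × 1.5 = 13.5 and 13 × 1.5 = 19.5.

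**3. Direction of the bias.** A likelihood model on T1 and T2 predicts each missing T2 from T1, using the relation seen in those who stayed. If people with high recent scores leave, those who stayed have lower T2 scores than others with the same T1, so the predicted T2 is too low and improvement is overstated. Completers also tend to start lower, which works the other way in their mean change, so the completer estimate has no fixed direction.

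**4. Size (simulation).** The documents give no SD, correlation or dropout model, so these inputs are assumed: N = 44, SD 4.5, true T1-T2 change −3.0, and odds of leaving that rise 2.1- or 2.7-fold per 5 points on the latest recorded score.

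| Loss | Odds per 5 points | When lost | Without weekly scores | With weekly scores |
|---|---|---|---|---|
| 30% | 2.1 | spread over weeks | −3.22 | −3.00 |
| 30% | 2.1 | after Week 4 | −3.37 | −3.02 |
| 30% | 2.7 | spread over weeks | −3.29 | −3.01 |
| 30% | 2.7 | after Week 4 | −3.46 | −3.01 |
| 20% | 2.1 | spread over weeks | −3.14 | about −3.00 |
| 20% | 2.1 | after Week 4 | −3.23 | about −3.00 |

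At 30% loss the excess runs from 3.22 − 3.00 = 0.22 to 3.46 − 3.00 = 0.46 points. Another assumed covariance gave −3.36 to −3.54 without the weekly scores, and −2.99 to −3.01 with them.

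**5. Stronger selection.** Assumed: SD 4.5, correlation between visits c + (1 − c) × 0.7^(weeks apart) with c = 0.3 or 0.5, and true change −2.0. The 9 or 13 people highest on a noisy Week 4 score miss T2 and T3. The likelihood model on T1-T3 gave −2.66 to −3.04, completers −2.24 to −2.49, and the model with weekly scores −1.98 to −2.05.

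**6. Leaving driven by a score never submitted.** True change −3.0, 30% loss, 2.1-fold odds: −3.37 to −3.39 without weekly scores and −3.20 to −3.24 with them. The remaining bias is 0.20-0.24 of 0.37-0.39, so half to two thirds of it stays.

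**7. Completers.** With a true change of −3.0, completer means across the assumed settings ran from −2.78 to −3.11.

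**8. Loss unrelated to symptoms.** No bias either way. The standard error changes little (0.88 to 0.84 in one setting).

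**The case against.** The strongest reply is that the plan does not exclude the weekly scores. Section 6.4 names them as efficacy data, the T1 to T2 (and T3) limit sits in the ANOVA sentence, and the mixed-model sentence that follows has no such limit. This stands. A reader might infer that the plan deliberately leaves the weekly scores out of every efficacy analysis, but the documents support only that no analysis names them. The gap remains, because the data-source list in 6.2, followed literally, leaves them out.

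Second, the ANOVA is the analysis named for T1-T2 change, and its completer estimate is off by little and in no fixed direction. This also stands, so the 0.2-0.5 point excess should not be attributed to the ANOVA.

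Third, recovery of the true change in steps 4 and 5 is built in, because leaving was made to depend on recorded scores. Step 6 shows what happens otherwise. A reader might infer that adding the weekly scores makes the loss missing at random; it only makes that assumption more plausible.

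Fourth, the gain is modest. A bias of 0.36 is 0.36/0.88 = 0.41 of its standard error, and root mean squared error fell from 0.95 to 0.85 in one setting and by only 0.03-0.08 in others. The trial is a single-arm pilot whose primary outcomes are benchmarks, and without a control arm the pre-post change cannot separate effect from time. That limits the stakes, but the remedy uses data already being collected.

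**Conclusion.** The concern holds as an unspecified use of collected efficacy data, together with a mismatch between the data-source list in Protocol 6.2 and section 6.4. The textual finding is firm.

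The size is not. If leaving depends on recent scores, a likelihood model on T1-T3 alone overstates a true 3.0-point improvement by roughly 0.2-0.5 points at 30% loss, and by less at the planned 20% (0.14 to 0.23 in step 4). These figures rest on an assumed SD of 4.5 and assumed odds of leaving; the stronger selection in step 5 gave more. If loss is unrelated to symptoms there is no bias.

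A reader might take all 176 forms as evidence on those who left. Most come from completers, and the relevant maximum is 36 to 52. The feasibility and acceptability benchmarks are untouched. What is affected is the preliminary effect estimate meant to inform later studies.

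**What to change.** 1. Reconcile Protocol 6.2 (Data analysis) with 6.4, so that both list the weekly surveys as a source for preliminary effects.
2. In Protocol 6.2 and 17.1 and in the SAP's Pre-Post Changes section, state that the Week 1-4 PHQ-9 and GAD-7 enter the mixed model as additional visits, with visit categorical.
3. Specify a covariance that 44 participants can support. An unstructured matrix has 7 × 8/2 = 28 parameters for seven visits, against 3 × 4/2 = 6 for three. A random intercept plus serial correlation that decays with the time between visits is one economical choice, since the visits are unequally spaced.
4. Make this model the main symptom analysis in place of the repeated measures ANOVA, with T1-T2 and T1-T3 as the reported contrasts.
5. Show the T1-T3-only fit as a sensitivity analysis, and tabulate the weekly scores by whether T2 was completed.

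The cost is a few sentences and a larger covariance model, with no new data, visits or participant burden. One check is needed: the protocol and SAP do not state the recall period of the weekly form, so if it differs from that at T1-T3, confirm that the difference does not drive the result.

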6.6 N/A

7.0 Data and Specimen Banking

- 7.1 De-identified data (i.e., data linked to PID) will be kept indefinitely after the completion of the study. These de-identified data include (1) data collected from T1, T2, T3, and weekly Qualtrics survey; (2) data from wearable devices (e.g., sleep duration, sleep activity); (3) de-identified data downloaded from Expiwell (e.g., timestamps of EMA completions and other adherence information); (4) de-identified interview and voice recording transcripts, with all potentially identifying information removed; and (5) de-identified data collected during Zoom screening interview (collected after consent). Access to the data will be restricted to authorized study personnel, including the principal investigator and designated research staff responsible for receipt, storage, and analysis of data. Screening data from the screening Qualtrics survey will not be stored or used for any other purposes. Qualtrics software will be accessible only to authorized study personnel. Identifiable consent information will be downloaded from Qualtrics and securely stored on Stronghold and will be deleted from Qualtrics once successful transfer and storage have been confirmed.

As described in section 6.2, video recordings of the exit interview will be deleted as soon as the audio can be downloaded from the Brown Zoom cloud and successfully uploaded to Stronghold. Audio of the interview will be deleted after the interviews are transcribed and vetted for accuracy by study staff. Audio recordings obtained through Expiwell will be downloaded and transferred to Stronghold. Audio will be deleted from Expiwell's cloud after it is successfully uploaded to Stronghold. These audios will be deleted from Stronghold after they are transcribed and vetted for accuracy by study staff. Therefore, we will only use deidentified transcripts of all audio data in analysis.

The crosswalk files linking PII to PID will be retained until either a manuscript utilizing the data is submitted for publication or for a period of 5 years after study completion (whichever comes first), consistent with institutional policy. This allows for the deletion of a participant's data upon request, at any time prior to dissemination.

Further, participants will be asked in the future contact form whether they would be interested in being contacted about future research studies in the lab. For participants who consent to being contacted in the future, we will retain their contact information in a separate file not linked to their PID for up to 5 years, after which point we will destroy the information.

- 7.2 Data that will be stored for future use will be de-identified and linked to each participant's unique PID. These include (a) Qualtrics survey responses from T1, T2, T3, and weekly assessments; (b) data from wearable devices (e.g., sleep duration, sleep activity); (c) study participation records (e.g., timestamps of survey or EMA completions and other adherence information); (d) de-identified transcripts of exit interviews and EMA voice recordings; and (e) de-identified data collected during Zoom screening interview (collected after consent). The password-protected file linking PID to participant name (described in Section 17.2) will also be destroyed 5 years after study completion.

- 7.3 Representatives of the institutional IRB or regulatory agencies may request to inspect all documents and records related to the study by contacting the study PI.

